3.3 Inclusion-Exclusion Criteria and General Study Population

Patients with non-muscle invasive bladder cancer who have undergone TURBT and are judged to be at an increased risk for recurrence are eligible if they are BCG naive or have completed previous BCG treatment >12 months prior to the most recent TURBT are eligible for both the phase 1 or 2 parts of the study. Patients must meet all of the following inclusion criteria to be enrolled into the study:

Inclusion Criteria

1. Willing and able to sign informed consent and comply with the protocol, including clinic visits to receive weekly vesigenurtacel-L injections for 12 doses followed by either monthly vesigenurtacel-L injections for three months in Phase 1 or three courses of three once-weekly injections in Phase 2.
2. Histologically or cytologically confirmed non-muscle invasive bladder cancer [Ta, T1 or Tis (CIS)]. Papillary disease must have been removed by transurethral resection or fulguration.
3. Either
 - i. High-risk disease, defined as T1 and/or high-grade and/or CIS, *or*
 - ii. Intermediate-risk disease defined as Ta low-grade with at least three of the following four risk factors: multiple tumors, tumor size > 3cm, early recurrence (<1 year from previous staging procedure), or recurrence with a frequency of more than once in any 12 month period.
4. Patients must be BCG naive or have completed previous BCG treatment >12 months prior to the baseline staging procedure.
5. For Phase 2 only: Arms 1, 2, and 3: Suitable, in the opinion of the investigator, to receive a 6-week course of induction intravesical BCG in the adjuvant setting within 6 weeks following the baseline staging procedure for the current occurrence of non-muscle invasive bladder cancer. Arm 4: Suitable for monotherapy vaccine administration post-TURBT. For Phase 1 only: Has previously received 3-6 weekly doses of BCG.
6. Age ≥18 years
7. Lab parameters:
 - Albumin ≥2.5 mg/dL
 - Total bilirubin <1.5 mg/dL
 - Alanine transaminase (ALT) and aspartate transaminase (AST) ≤2.5 × upper limit of normal (ULN)
 - Serum creatinine ≤2.2 mg/dL or calculated creatinine clearance >35 mL/minute per the Cockcroft-Gault formula
 - White blood cell (WBC) count ≥4,000/mm³ with an absolute neutrophil count ≥1,500/mm³
 - Hemoglobin ≥9 g/dL
 - Platelet count ≥75,000/mm³
8. Women of childbearing potential or men of fathering potential must use adequate birth control measures (e.g., abstinence, oral contraceptives, intrauterine device, barrier method with spermicide, or surgical sterilization) during the study and for 6 months after receiving the last administration of study medication. Female patients of childbearing potential must test negative for pregnancy prior to enrolling in the trial.

Exclusion Criteria

Patients that meet any of the following exclusion criteria are not eligible to be enrolled into the study:

1. Known human immunodeficiency virus (HIV) infection or other immunodeficiency disorders, either primary or acquired
2. Infections or concurrent illness, requiring active therapy
3. Any condition requiring active steroid or other immunosuppressive therapy
4. Active malignancies within 12 months with the exception of those with a negligible risk of metastasis or death treated with expected curative outcome
5. Prior prostatic pelvic radiation within the past 12 months
6. Known history of clinically significant cardiac impairment, congestive heart failure > New York Heart Association (NYHA) cardiac disease classification Class II, unstable angina, or myocardial infarction during the previous three months
7. Known current alcohol or chemical abuse, or mental or psychiatric condition precluding compliance with the protocol
8. Pregnant or nursing
9. Known allergy to soy, egg, or peanut products
10. Receiving another investigational agent (30 day wash-out required prior to first dose)
11. Neo-adjuvant therapy prior to the baseline staging procedure for the current occurrence of non-muscle invasive bladder cancer
12. Prior treatment with a cancer vaccine for this indication
13. Prior vaccination with BCG for tuberculosis disease
14. Prior splenectomy

3.4 Randomisation and Blinding

Patients will be randomized to Arms 1-3 centrally using a randomized block design, stratified for risk of recurrence (strata: high vs. intermediate risk) and CIS (strata: yes vs. no). The intent for stratification is to ensure balance between treatment groups with respect to these important prognostic factors. A block size of 3 was chosen to control for potential imbalance between the three treatment groups. Given the limited sample size, a formal subgroup analysis based on the stratification variables will not be undertaken. Patients who will not receive BCG will be consecutively allocated (non-randomized) into Arm 4 consisting of vaccine monotherapy.

Protocol Version 7.0 was updated to allow a temporary revision to the randomization algorithm due to delays in the batch release of certain doses of vaccine. This allowed the randomization schedule to be temporarily revised from a 1:1:1 randomization to a 1:1 randomization, with one arm being briefly

suspended. The batch was released in time such that this change was never implemented; the randomization algorithm was never changed during the study.

The randomization schedule will be prepared by an independent statistician not otherwise involved with this study, and will be implemented through an interactive web based system. The study will be single-blinded (physician-patient).

3.5 Study Variables

In general, the schedules of assessments (SOA) are divided into an induction and maintenance phase.

In the phase 1 component of the study, the induction phase will consist of 6 weekly vaccine doses, a one week drug free period and then followed by 6 more weekly doses. The maintenance phase will then consist of monthly treatments for 3 doses for up to a total of 15 doses, unless the criteria for treatment discontinuation are met.

In the phase 2 component of the study, the induction phase will consist of 6 weekly HS-410 (or placebo) doses in combination with 6 doses of BCG, followed by 6 weeks of HS-410 or placebo monotherapy with a vaccine holiday on Week 13 to allow for disease assessment. This will be followed by a maintenance phase consisting of 3 courses of three once-weekly injections in combination with intravesical maintenance BCG for a total of 21 doses, unless the criteria for treatment discontinuation are met. Additional maintenance therapy will be at the discretion of the treating physician.

Current Schedule of Assessments for each study are contained in the study protocol.

Study Day and Visit Windows

Patients' time on study will be determined in Study Days. Study Day 1 will be defined as the first day of dosing. Positive study days will count forward from Study Day 1. Study Day -1 will be the day before Study Day 1, and all subsequent negative study days will be measured backward from Study Day -1. There will be no Study Day 0.

A value obtained on Study Day 1 before administration of study treatment will be considered the baseline value. If a value is not available on Study Day 1, the last available value collected prior to the first dose of study drug will be used as the baseline value. The study date and corresponding study visit will be captured on each case report form (CRF) from which study day will be calculated.

Study Day will be used in the analysis of safety data and efficacy analysis. The protocol allows a 3-day window between randomization and first dose. All efficacy analyses on time-to-event endpoints will consider the date of randomization as Day 1.

4 Sample Size

Phase 1

Phase 1 is designed to provide some indication of safety and tolerability of the low dose of HS-410 as a monotherapy. A sample size of 10 patients in the monotherapy setting is deemed suitable for an assessment of safety.

Phase 2

The objective of the phase 2 study is to compare 1-year disease free survival of two doses of HS-410 + BCG versus BCG + placebo in patients with non-muscle invasive bladder cancer who have undergone TURBT. Given the phase 2 exploratory nature of the study, the overall level of significance will be 0.10, using a one sided test with no adjustment for multiplicity, 75 patients will be randomized in a 1:1:1 (low dose HS-410 plus BCG and high dose HS-410 plus BCG vs. plus BCG + placebo) ratio to yield 69 evaluable (23 patients per arm). 25 patients will be enrolled into the monotherapy arm. Under the assumption that the one-year disease-free survival rate in the control is 60%, the study will have an 80% power to detect a 30% absolute difference between the two experimental groups and the control. Patients will be followed for three years after the last patient has been enrolled and patients will be obtained from approximately 20 participating centers.

5 Statistical Considerations

5.1 General Principles

All statistical analyses will be performed using SAS® Version 9.4 (or later). At the end of the study for both phase 1 and 2, individual data listings and descriptive statistics will be provided by treatment group.

Descriptive statistics for continuous variables will include number of subjects (n), mean, standard deviation (SD), minimum, median, and maximum, unless specified otherwise.

Descriptive statistics for categorical variables will include frequency counts and percentages [N (%)]. Unless stated otherwise, the denominator for percentage calculations will be the number of subjects in the analysis set.

The mean, median (if needed), standard deviation, and any other statistics other than quantiles, will be reported to one decimal place greater than the original data. The minimum and maximum will use the same number of decimal places as the original data.

P-values ≥ 0.001 will be reported to 3 decimal places; p-values less than 0.001 will be reported as " <0.001 ". Estimated parameters, not on the same scale as raw observations (e.g. regression coefficients) will be reported to 3 significant figures.

There will be no imputation of missing data.

All data will be listed, sorted by site, treatment and subject, and when appropriate by visit number and/or visit date within subject. All summary tables will include a column for each treatment group in the order (Control, Experimental) and will be annotated with the total population size relevant to that table/treatment, including any missing observations.

5.2 Analysis Populations

5.2.1 Phase 1

Safety Population

- Safety Population is defined as all patients receiving at least one dose of HS-410

5.2.2 Phase 2

Intent-to-Treat (ITT) Population

- The intent-to-Treat (ITT) population is defined as all patients randomized into the study and who will be classified according to their assigned treatment group, regardless of the actual treatment received. This population will be used for the primary efficacy analyses, and all analyses of patient disposition, demographics and baseline disease characteristics.

Safety Population

- The safety population will be defined as all randomized patients who receive at least one dose of treatment (BCG, HS-410, or any combination thereof), and be referred to as the “Safety Population”

Per Protocol Population

- The Per Protocol (PP) population is defined as all randomized/enrolled patients in the ITT population who do not have any major protocol deviations. All major protocol deviations will be reviewed by Data Monitoring Committee (DMC) prior to database lock and unblinding. Patients will be excluded from this population if the DMC determines the major protocol deviation may impact on the efficacy outcomes of the patient.

Analysis Population for Exploratory Endpoints

Patients completing at least 6 weekly doses of study medication

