#### **6.2.3.2 Phase 2 Assessments at Week 1 (Day 1)**

The following procedures will be performed after all the previous baseline procedures have been completed:

- Study product administration
  - Initiate series of weekly study product dosing (dosing should begin within 6 weeks of baseline staging procedure)
  - Initiate series of weekly BCG dosing (Arms 1-3 only)
  - Monitor patient on site for potential acute reactions for 30 minutes after study product administration
- Record adverse events
- Record concomitant medications
- Send at least 4, non-stained, 10 micron sections from baseline staging procedure for evaluation of antigen expression. If slides are not available, formalin-fixed, paraffin-embedded (FFPE) tissue ( $\geq 50$  microns) is also acceptable.

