### **6.2.3.14 Phase 2 Week 56 (Day 386 ±3) – End of Treatment Visit (4 weeks post last dose)**

The following procedures should be completed approximately four weeks following last dose of study product including patients who discontinue study product dosing prematurely.

- Physical exam (full examination as well as weight and vital signs)
- 12-lead ECG

- Blood and urine collection for immune monitoring
- Hematology, chemistry with LDH, and dipstick urinalysis
- Urine or serum pregnancy test for female patients of childbearing potential
- Autoimmune Labs (ANA, TSH, ESR, and C-reactive protein are required; RF, T3, T4, and thyroid antibodies if clinically indicated)
- Autoimmune Phenomena – Assessment of adult autoimmune system disorders (including: eye exam for dry eyes, lymph node and joint assessment for swelling, and skin exam for vitiligo and rash)
- Record concomitant medications
- Record adverse events

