### Phase 2:

Intent-to-Treat (ITT): defined as all patients randomized into the study and who will be classified according to their assigned treatment group, regardless of the actual treatment received.

Safety Population: defined as all randomized patients who receive at least one dose of treatment (BCG, HS-410, or any combination thereof)

Per-protocol population: defined as all patients in the ITT population who do not have any major protocol deviations (including being non-compliant to the study drug)

Other sub-populations of patients for secondary and exploratory analyses may be defined at the time of statistical analysis and will be identified in any reporting of results.

Patients will be randomized to Arms 1-3 centrally using a stratified block design according to risk of recurrence (strata: high vs. intermediate risk) and CIS (strata: yes vs. no). The intent for stratification is to ensure balance between groups with respect to these important prognostic factors. Given the limited sample size, a formal subgroup analysis based on the stratification variables will not be undertaken. Patients who will not receive BCG will be consecutively allocated (non-randomized) into Arm 4 consisting of vaccine monotherapy.

Due to delays in the batch release of certain doses of vaccine, the randomization schedule may be temporarily revised from a 1:1:1 randomization to a 1:1 randomization, with one arm being briefly suspended. During the period of revised randomization, each patient will maintain at least a 50% chance of receiving vaccine versus placebo. Randomization strata will remain unchanged. Upon batch release of the vaccine the randomization will return to the original 1:1:1 ratio. In order to maintain the study blinding, temporary closure of certain arms will not be disclosed outside of the DMC except as needed for Informed Consent documents.

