#### **12.5.2.8 Immune Response**

Section 10.2.1 details how samples are run in duplicate or triplicate using ICS via flow cytometry or ELISPOT. The first step in the analysis of immunologic response will be to form the subject average across the duplicate or triplicate measurements recorded at each time point. In situations where only one measurement is obtained, the single value will be used in the analysis. If any values are in the range (0,1) inclusive, a value of 0.5 will be used in the analysis of count information on the log10 scale.

The observed and log10 transformed values will be summarized for each visit. In addition, the change from baseline will also be summarized descriptively. At each visit and for the last available visit, a sign-rank test will be used to evaluate the null hypothesis that the change from baseline is centered at zero separately for each of the dosing groups. Similarly, a Wilcoxon rank-sum test will be used to evaluate the null hypothesis that the observed and change from baseline values have a similar location ((i.e. median) between the low and high dose groups.) A 95% CI for the ratio of the differences geometric mean will be obtained by back-transforming the 95% non-parametric CI for the difference in log10 analysis. For the purposes of identifying the most important comparison, the analysis of the last assessment will be considered the primary analysis with other time points considered secondary analyses. Additionally, a repeated measures analysis will be completed modeling log10 transformed values as a function of visit, treatment, and a visit

by treatment interaction. Model results may not be reported if convergence is unattainable because of the small sample size.

These analyses will be completed using the ITT and Per-Protocol populations.

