- Proportion of patients with progressive disease at 3, 6, 12, 18, and 24 months from randomization. Progressive disease is defined as an increase in T stage from TIS or Ta (at screening) to T1 (lamina propria invasion), development of T2 or greater or lymph node (N+) disease or distant metastasis (M1), or an increase in grade from low to high per the IBCG recommendations.
- Disease-Free survival at 3, 6, 18, and 24 months from randomization. A patient is considered as disease-free at a timepoint if the disease has not recurred nor progressed, and the patient is still alive.
- Overall Disease free survival (DFS): DFS is the time from randomization until the day of disease recurrence or progression
- Overall survival (OS): OS is the time from randomization until the day of death by any cause or censoring
- Proportion of patients undergoing a repeat TURBT by 12 months and by 24 months from randomization
- Proportion of patients undergoing cystectomy by 12 months and by 24 months from randomization
- Immunological response (IR): Peripheral blood immunological response via intracellular cytokine staining (ICS) by ELISPOT of on CD8+ cells following HS-410 vaccination will also be evaluated

Phase 2 only:

- Safety of the combination of vesigenurtacel-L and BCG
- Safety of high dose vesigenurtacel-L monotherapy

Exploratory Endpoints

In patients completing at least 6 weekly doses of study medication, the following exploratory endpoints will be evaluated:

- Immunologic response of PBMCs (analysis of surface markers, CD3, CD4, CD8, degranulation) and stimulation analysis via ICS of IFN- γ , IL-2, TNF α and perforin.
- Total PBMC counts by flow cytometry, including lymphocyte subsets (B cells, helper T-cells, cytotoxic T-cells, NK cells and T-reg)

- Evaluation of tumour tissue obtained from pre-treatment resection for antigen expression by immunohistochemical analysis
- Evaluation of tumour tissue obtained from repeat biopsy, if clinically indicated, for presence of infiltrating T-lymphocytes
- T cell receptor sequencing of peripheral blood T cells before and during the course of treatment
- Immune cell infiltration and inflammatory cytokine levels in urine (phase 2 only)

Safety Endpoints

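### SAP 2.1 and 5.2.2 confine every listed exploratory endpoint, even pre-treatment tumour antigen expression, to patients who completed at least six weekly doses

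*SAP*

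**What the plan says.** SAP 5.2.2 names one population for exploratory endpoints: "Patients completing at least 6 weekly doses of study medication". SAP 2.1 repeats it at the head of the list: "In patients completing at least 6 weekly doses of study medication, the following exploratory endpoints will be evaluated". No endpoint is exempted. The list includes "Evaluation of tumour tissue obtained from pre-treatment resection for antigen expression by immunohistochemical analysis", alongside PBMC, T-cell receptor, repeat-biopsy and urine endpoints. SAP 7.3 then lists these endpoints again without the six-dose condition and leaves summaries and exploratory analyses to a separate plan.

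The protocol contains no six-dose rule. Under Protocol 6.2.3.2 (Week 1) sites are told: "Send at least 4, non-stained, 10 micron sections from baseline staging procedure for evaluation of antigen expression". Blood and urine for immune monitoring are taken at baseline (6.2.3.1). They are taken again at the End of Treatment visit, which applies to everyone, "including patients who discontinue study product dosing prematurely" (6.2.3.14).

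**The concern.** In the randomised arms, reaching six doses depends partly on the assigned treatment. Protocol 7.2.1 requires stopping for a related Grade 4 event and for a Grade 3 or greater allergic or autoimmune reaction. Either could occur at different rates on low dose, high dose and placebo. Summaries by arm within the six-dose set therefore no longer describe the groups as randomised.

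The direction of any distortion is open. Removing patients who stopped before mounting a response raises an apparent response rate. Removing patients who stopped because of a strong immune reaction could lower it.

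For tissue resected before the first dose, later dosing cannot affect the measurement, so the filter can only remove information. It also sits oddly with SAP 5.2.2 itself, which assigns the ITT population to disease characteristics at baseline. Finally, because 2.1 and 5.2.2 carry the restriction and 7.3 does not, a programmer cannot tell which set applies.

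**Working it through.** **Plan figure.** The plan gives no figure for this point. Its only sizing figure, 80% power for 60% versus 90% with 23 evaluable per arm and one-sided alpha 0.10, is reproduced by an exact one-sided Fisher calculation (80.8%). Nothing below depends on it.

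**Who is excluded.** In Phase 2, dose 6 falls at Week 6 (Protocol 6.2.3.3) and the first scheduled cystoscopy and cytology at Week 13 (6.2.3.6). In Phase 1 they fall at Weeks 6 and 7. No scheduled disease assessment precedes dose 6, so early stopping will mostly reflect toxicity, illness or withdrawal.

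**How many.** The documents do not say. Protocol 12.6.2 assumes 10% drop-out over the whole study, and Protocol 7.2.4 describes its 10% overage as covering missing data and discontinuation for reasons other than disease or toxicity. Neither is a rate of stopping before dose 6. With an assumed share d, the set has 25 × (1 − d) patients per arm on average:

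| Assumed d | Per arm | Excluded of 75 |
|---|---|---|
| 0% | 25 | 0 |
| 5% | 23.75 | 3.75 |
| 10% | 22.5 | 7.5 |
| 20% | 20 | 15 |

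**Effect on one arm (assumption: 10 of 25 are true responders and 2-3 stop early).**
- All patients: 10/25 = 40.0%.
- All early stoppers are non-responders: 10/23 = 43.5% or 10/22 = 45.5%, a rise of 3.5 to 5.5 points.
- Opposite extreme, all early stoppers are responders: 8/23 = 34.8% or 7/22 = 31.8%, a fall of 5.2 to 8.2 points.
- 95% half-width for 10/25, normal approximation: 1.96 × √(0.4 × 0.6 / 25) = 19.2 points.

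**Effect on a between-arm difference (all values assumed).** True marker positivity is 30% in both arms, all early stoppers are negative, and 5% of control patients stop early. The control arm shows 0.30/0.95 = 31.6%.

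| Active arm stopping early | Active arm shows | Spurious difference |
|---|---|---|
| 5% | 0.30/0.95 = 31.6% | 0 points |
| 10% | 0.30/0.90 = 33.3% | 1.8 points |
| 15% | 0.30/0.85 = 35.3% | 3.7 points |
| 20% | 0.30/0.80 = 37.5% | 5.9 points |

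For comparison, the 95% half-width of a difference at 30% with 25 per arm is 1.96 × √(2 × 0.3 × 0.7 / 25) = 25.4 points.

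**The case against.** The case for leaving the rule alone has substance.

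- **The protocol permits it.** Section 12.2 states: "Other sub-populations of patients for secondary and exploratory analyses may be defined at the time of statistical analysis". That stands as permission. It supplies no reason, and the SAP makes the six-dose set the only named set rather than a supplement.
- **There is a precedent.** Protocol 1.4 reports that the earlier lung cancer vaccine study characterised immune response in patients who had received at least one six-week course. This is a fair reason to keep the set for post-dose immune endpoints, but not for baseline tissue.
- **Few patients may be affected.** Twelve weekly doses are planned and the rule does not require the first six in sequence, so a patient who misses an early dose can still qualify. This stands.
- **Little inference is planned.** SAP 5.5 gives exploratory endpoints estimates and intervals without p-values. Protocol 12.1 does mention between-group tests, but as an aid to review. Estimates carry the same selection as tests, but the stakes are low.
- **The alternative is also selective.** Requiring a post-dose sample is itself partly a post-randomisation condition. The first scheduled one is at Week 7, so the two sets will largely coincide. This stands, and is why exclusions should be counted by arm.

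A reader might infer more than the documents support:

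- *Samples are thrown away.* SAP 5.1 lists all data, and nothing says samples are destroyed or left unassayed.
- *Treatment failures are selected out.* No scheduled assessment could identify them before dose 6, and patients with evidence of disease may continue treatment.
- *Patients with poor outcomes are removed from the antigen question.* Protocol 10.2.6 plans to correlate antigen expression with immune response, not with recurrence.
- *The SAP contradicts Protocol 12.5.2.8*, which says "These analyses will be completed using the ITT and Per-Protocol populations". That section governs the secondary immune-response endpoint, which the six-dose rule does not cover.

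**Conclusion.** The point holds as a minor defect in the exploratory population. The restriction is explicit, covers every listed exploratory endpoint, has no rationale for pre-treatment tissue, leaves out patients from whom usable samples are collected, and is missing from SAP 7.3. The post-randomisation argument applies to Arms 1-3 only, since Arm 4 is not randomised.

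The size of any bias is unknown. It is zero if nobody stops before dose 6. Under the assumption that 2-3 of 25 stop and all are non-responders, 40.0% reads as 43.5-45.5%; the opposite extreme moves it down by up to 8.2 points. Either is small beside a half-width of about 19 points, although a selection effect is not averaged out as sampling error is. It would be wrong to conclude that the trial's randomised comparison is compromised: the primary ITT analysis, its power and the secondary analyses do not use this set.

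**What to change.** Amend SAP 2.1 and 5.2.2 as follows:

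1. Analyse pre-treatment tissue endpoints in all patients with tissue.
2. Analyse change-from-baseline endpoints by assigned arm in all patients with a baseline and at least one post-dose sample. Report the number excluded per arm, because this set too is partly defined after randomisation.
3. Keep the six-dose set as a labelled sensitivity analysis.
4. State the same populations in SAP 7.3 and carry them into the separate exploratory plan.

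The cost is SAP wording and a few extra assays on samples the protocol already collects. The drawback is that some added patients will contribute only an off-schedule End of Treatment sample after few doses; the sensitivity analysis shows whether that matters.
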